6.2.7 Population Pharmacokinetics

Pharmacokinetic blood samples will be collected at 3 study visits, and collection of these samples will be limited to days when blood draws are already scheduled for other purposes (ie, clinical safety laboratory tests). The data collected during this trial will be used to explore the relationship between pharmacokinetic parameters and covariates, such as body weight, age, and other factors as appropriate. Because pharmacodynamic endpoints are also being measured during the study, concentration-response relationships may also be investigated.

6.3 Premature Termination or Suspension of Study or Investigational Site

6.3.1 Criteria for Premature Termination or Suspension of the Study

The study will be completed as planned unless one or more of the following criteria are satisfied that require temporary suspension or early termination of the study:

- New information or other evaluation regarding the safety or efficacy of the study medication that indicates a change in the known risk/benefit profile for the compound, such that the risk/benefit is no longer acceptable for subjects participating in the study.
- The Data Monitoring Committee recommends that the study should be suspended or terminated.
- Significant violation of Good Clinical Practice (GCP) that compromises the ability to achieve the primary study objectives or compromises subject safety.

6.3.2 Criteria for Premature Termination or Suspension of Investigational Sites

A study site may be terminated prematurely or suspended if the site (including the investigator) is found in significant violation of GCP, protocol, or contractual agreement, is unable to ensure adequate performance of the study, or as otherwise permitted by the contractual agreement.

6.3.3 Procedures for Premature Termination or Suspension of the Study or the Participation of Investigational Site(s)

In the event that the sponsor, an IRB/IEC or regulatory authority elects to terminate or suspend the study or the participation of an investigational site, a study-specific procedure for early termination or suspension will be provided by the sponsor; the procedure will be followed by applicable investigational sites during the course of termination or study suspension.

7.0 SELECTION AND DISCONTINUATION/WITHDRAWAL OF SUBJECTS

All entry criteria, including test results, need to be confirmed prior to randomization. If necessary, any diagnostic testing needed to confirm hypertension classification (ie, secondary or primary) must be completed before the Wash-out/Placebo Run-in.

7.1 Inclusion Criteria

Subject eligibility is determined according to the following criteria:

1. In the opinion of the investigator, the subject or parent/legal guardian is capable of understanding and complying with the protocol requirements.
2. The subject is capable of understanding (as far as their cognitive ability allows and as judged by the investigator and parent/legal guardian) an informed assent form or consent form (if of an appropriate age) and verbal explanations by the investigator. The subject is willing to give their written assent (if required by IRB/IEC) or consent (if of an appropriate age) to participate.
3. The subject's parent/legal guardian, if signing consent on behalf of their child, must (1) have understood the information contained in the informed consent document and had an opportunity to ask questions of the investigator and understands the answers, and (2) sign and date a written informed consent form on behalf of their child prior to the initiation of any study procedures.
4. The subject has hypertension (primary or secondary) defined as clinic seDBP \geq 95th percentile (by age, gender, and height) or \geq 90th percentile (by age, gender, height) if chronic renal disease, diabetes, heart failure or hypertensive target organ damage is present.
 - a) If currently treated: The subject has a documented historical diagnosis of hypertension AND a post-washout clinic seDBP meeting the above criteria on Day -1 (or Day 1 for subjects not participating in ABPM).
 - b) If currently untreated: The subject has elevated seDBP meeting the above criteria on 3 separate occasions before Randomization, including on Day -1 (or Day 1 for subjects not participating in ABPM).
5. The subject is male or female and aged 6 to $<$ 18 years at Baseline and weighs at least 25 kg.
6. Subjects $<$ 50 kg must have the ability to swallow a capsule or tablet with a maximum size of 15.64 mm in length and 7.42 mm in thickness, while subjects \geq 50 kg must have the ability to swallow a tablet or capsule with a maximum size of 16.19 mm in length and 8.30 mm in thickness.
7. The subject agrees to continue their previously implemented nonpharmacological life style modifications if begun prior to Screening. Note: For subjects participating in a weight loss program, the weight maintenance phase must have begun at least 30 days prior to Screening/Visit 1.

8. Subjects may be renal transplant patients if time post-transplant has been greater than 6 months prior to Screening, with stable graft function (and eGFR ≥ 30 mL/min/1.73 m²) for at least 6 months, stable use of immunosuppressive therapy for at least 30 days prior to Screening, and documented evidence that there is no transplant renal artery stenosis.
9. All female subjects who are of child bearing potential* (defined as females aged ≥ 12 years old and younger females who, at the discretion of the investigator, are deemed to be of reproductive potential) who are sexually active agree to routinely use adequate contraception* from Screening until the last dose of study medication. All female subjects aged ≥ 12 years old and younger females who, at the discretion of the investigator, are deemed to be of reproductive potential must provide a negative serum pregnancy test at Screening and a negative urine pregnancy test at Day 1.

*Definitions and acceptable methods of contraception are defined in [Section 9.1.9](#)
Contraception and Pregnancy Avoidance Procedure and reporting responsibilities are
defined in [Section 9.1.10](#) Pregnancy.

10. The subject is untreated, or willing, and in the opinion of their treating physician, can safely be withdrawn from previous antihypertensive medications for a maximum of 4 weeks (if a washout extension is required) prior to randomization.
11. The subject has clinical laboratory results (including clinical chemistry, hematology, and complete urinalysis) within the reference range for the testing central laboratory unless the results are deemed by the investigator to be stable and related to the subject's medical history and/or not clinically significant, with the exception of hyperkalemia or pertinent electrolyte disorders (exclusion criterion 16). Subjects with LFTs under the values specified by exclusion criterion 15 may be included provided the subject does meet the other criteria stated in that exclusion (i.e. active liver disease, jaundice and severe hepatic impairment),

7.2 Exclusion Criteria

Any subject who meets any of the following criteria will not qualify for entry into the study:

1. The subject has a clinic seated SBP greater than 15 mm Hg and/or DBP greater than 10 mm Hg above the 99th percentile for age, gender, and height as confirmed by the average (arithmetic mean) of 3 serial clinic seated blood pressure measurements at Screening/Visit 1.
2. The subject has a diagnosis of malignant or accelerated hypertension.
3. The subject is currently treated with more than 2 antihypertensive agents.
4. The subject or parent/legal guardian is not willing for the subject's previous antihypertensive medications to be stopped.
5. The subject has participated in the intensive, active weight-loss phase of a weight-loss program within 30 days prior to Screening/Visit 1.

6. The subject was noncompliant (<70% or >130%) with single-blind study medication during the Placebo Run-in.
7. The subject is currently participating in another interventional study or has taken an investigational drug within 30 days prior to Screening/Visit 1.

NOTE: This criterion does not apply to subjects who participated in a single-dose AZM study, nor does it apply to subjects who participated in observational studies that lacked an intervention or invasive procedure.
8. The subject or parent/legal guardian is an immediate family member, study site employee, or is in a dependent relationship (eg, spouse, parent, child, sibling) with a study site employee who is involved in the conduct of this study.
9. If female, the subject is pregnant or lactating or intending to become pregnant before or during participation in this study.
10. The subject has any of the following: severe renal impairment (eGFR <30 mL/min/1.73 m² by the Schwartz formula [42]); is currently undergoing dialysis treatment; renovascular disease affecting both kidneys or a solitary kidney; severe nephrotic syndrome not in remission; or serum albumin <2.5 g/dL.
11. The subject has a history or clinical manifestations of severe cardiovascular, hepato-biliary, gastrointestinal, endocrine-metabolic (eg, hyperthyroidism, Cushing's syndrome), hematologic, immunologic, genito-urinary, or psychiatric disease, cancer, and/or any conditions that would interfere with the health status of the subject through study participation, or would jeopardize study integrity in the opinion of the investigator.
12. The subject is suffering from uncorrected coarctation of the aorta, or hemodynamically significant left ventricular outflow tract obstruction due to eg, aortic valvular disease, or is likely to undergo a procedure known to affect blood pressure (eg, repair of arterial anomalies) during the course of the study.
13. The subject has a history and/or presence of a clinically significant abnormal 12-lead ECG that is not related to medical history and/or concomitant diseases and is indicative of an unstable condition as determined by the investigator or sponsor/designee.
14. The subject is poorly controlled diabetic defined as having a glycosylated hemoglobin (HbA1c) value >8.5% at Screening/Visit 1.
15. The subject has alanine aminotransferase (ALT) or aspartate aminotransferase (AST) ≥2.5 times the upper limit of normal, or total bilirubin ≥1.5 times the upper limit of normal, severe hepatic impairment, active liver disease of any etiology, or jaundice at Screening/Visit 1 (exception may be made for subjects with Gilbert's disease, as long as subjects do not have active symptoms, such as indicated above).
16. The subject has hyperkalemia as defined by the central laboratory's normal reference range or any pertinent electrolyte disorders at Screening/Visit 1.

17. The subject has a known history of hepatitis B, hepatitis C or human immunodeficiency virus infection at Screening.
18. The subject has a known hypersensitivity or allergy to any angiotensin type II receptor blockers or to any of the excipients in AZM or losartan formulations to be taken
19. The subject has a history of drug or alcohol abuse within 1 year prior to Screening/Visit 1 or positive urine drug/alcohol screen test result at Screening/Visit 1. Subjects ≥ 12 years of age or younger children if deemed necessary by the investigator and their parents/legal guardians are required to give consent to urine alcohol/drug screen testing to be considered for eligibility. Subjects who have a positive drug screen for known physician prescribed medications (e.g. amphetamines for ADHD), are not abusing the medication in the investigator's judgment and are not an excluded medication are eligible for the study.
20. The subject has taken or requires the use of any medications or supplements within the stated time periods that are excluded, unable to washout excluded medications or not on a stable dose as described in the Excluded Medications or Concomitant Medications sections of this protocol.

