6.2 Justification for Study Design, Dose, and Endpoints

6.2.1 Patient Selection

In the US, the overall prevalence of childhood hypertension is 2% to 5%, making it one of the most common chronic diseases of childhood [5]. Similarly, the overall prevalence of pediatric hypertension in European countries generally ranges between 2% to 4% [6-9]. The causes of pediatric hypertension are diverse and age dependent: in infants and children, hypertension is usually secondary to an underlying disorder, most commonly renal parenchymal or renovascular disease [10-13]. In older children and adolescents, primary hypertension is more prevalent and often associated with overweight or obesity [14-17].

The targeted percentage of subjects with secondary hypertension randomized in this study will be at least 20%. Accordingly, many subjects are anticipated to have hypertension associated with underlying CKD. However, subjects with severe renal impairment (eGFR <30 mL/min/ 1.73 m²) or renal artery stenosis (unilateral or bilateral) will be excluded, as maintenance of adequate eGFR in patients with this condition is highly dependent on AII activity; subjects with hypertension secondary to uncorrected coarctation of the aorta will also be excluded. Subjects who are renal transplant patients will be allowed to enroll as long as renal graft function and immunosuppressive therapy (which alter BP) are stable. To maintain generalizability of the study results, the percentage of renal transplant patients will be monitored via IVRS/IWRS and a cap will be applied to maintain enrollment below ≈25%.

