9.1.14 Documentation of Randomization and Run-in Failure

Only subjects who meet all of the inclusion criteria and none of the exclusion criteria are eligible for randomization into the treatment phase. The IVRS/IWRS will be contacted for treatment assignment and this information should be captured on the appropriate eCRF.

If the subject is found to be not eligible for randomization, the investigator should record the primary reason for failure on the applicable eCRF. If the subject has begun the single-blind placebo run-in study medication, they are considered a run-in failure. The investigator should complete the appropriate eCRFs and register the subject as a run-in failure in the IVRS/IWRS.

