For subjects who did not participate in the ABPM procedure, if the subject's seDBP remains <95 th percentile for age, gender, and height or <90 th percentile by age, gender, height if chronic renal disease, diabetes, heart failure or hypertensive target organ damage is present after the Washout/Placebo Run-in Phase (ie, does not satisfy inclusion criterion #4 on Day 1), the washout may be extended in 1-week increments up to 2 times (currently treated subjects only), for a maximum possible washout of 4 weeks, as long SBP also remains below this threshold. Placebo should be continued during the extension(s). Subjects whose seDBP remains below the entry criteria after the extensions will not be eligible for randomization to the DB Phase and shall be discontinued from the study and referred back to their treating physicians to resume appropriate antihypertensive treatment.

If the subject has satisfied all of the inclusion criteria and none of the exclusion criteria for randomization, the subject should be randomized using the IVRS/IWRS system, as described in [Section 8.3](#). The procedure for documenting run-in failures is provided in [Section 9.1.14](#).

9.3.4.2 Double-Blind Phase-Week 2/Visit 5

Visit can occur within a \pm 2 day window. The following procedures will be performed.

- Vital signs (including standing measurements).
- Concomitant medications.
- AE assessment.
- Urine pregnancy test performed at the site (female subjects \geq 12 years old and younger females deemed by the investigator to be of reproductive potential).
- Pregnancy avoidance counseling (female subjects \geq 12 years old and younger females deemed by the investigator to be of reproductive potential).
- Collection of double-blind study medication and compliance assessment. If required, counsel subject or parent/legal guardian on compliance.
- IVRS/IWRS access to dispense double-blind study medication and register study visit.
- Administration of the first dose of the newly assigned double-blind study medication in the clinic.
- Dispensing of new supply of double-blind study medication with dosing instructions.

9.3.4.3 Double-Blind Phase-Week 4/Visit 6

Visit can occur within a \pm 2 day window. The following procedures will be performed.

- Vital signs (including standing measurements).
- Concomitant medications.
- AE assessment.
- Clinical laboratory tests (renal subpanel).
- Pharmacokinetic sampling.

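### Section 6.2.1 excludes one-sided renal artery stenosis, but exclusion criterion 10 does not, and every double-blind arm gives an ARB

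*Protocol*

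**What the plan says.** Protocol Section 6.2.1 (Patient Selection) says that subjects with "renal artery stenosis (unilateral or bilateral) will be excluded", and gives the reason: "maintenance of adequate eGFR in patients with this condition is highly dependent on AII activity".

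Exclusion criterion 10 in Section 7.2 lists several renal conditions. On renovascular disease it covers only "renovascular disease affecting both kidneys or a solitary kidney". The main exclusion criteria in the Study Summary (Section 2.0) use the same words.

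Inclusion criterion 8 asks for "documented evidence that there is no transplant renal artery stenosis", but only for renal transplant recipients.

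**The concern.** The rationale and the operative criterion disagree about one group: children with two kidneys, no transplant and known stenosis on one side. Section 6.2.1 shuts them out without qualification. No numbered criterion does.

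This is a safety matter in a paediatric trial. The protocol itself says why these children should not be enrolled, and the drug class it is worried about is given in every double-blind arm. Randomization cannot steer such a child to a non-ARB treatment, and those who continue receive azilsartan medoxomil (AZM) through the 44-week open-label phase.

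**Working it through.** No power, alpha or sample-size figure is involved. The check is a comparison of texts plus two counts.

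**Step 1: which text decides entry.** Section 7.1 opens with "Subject eligibility is determined according to the following criteria". Section 9.1.14 says: "Only subjects who meet all of the inclusion criteria and none of the exclusion criteria are eligible for randomization into the treatment phase". Section 9.3.4.1 goes further: "If the subject has satisfied all of the inclusion criteria and none of the exclusion criteria for randomization, the subject should be randomized". Section 9.3.1 also sends sites to Section 7.0 for screening. The numbered criteria therefore govern in practice.

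**Step 2: the two texts side by side, by type of child.**

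| Child with known stenosis | Section 6.2.1 | Section 7 criteria |
|---|---|---|
| Both kidneys affected | Excluded | Excluded (exclusion 10) |
| Solitary kidney affected | Excluded | Excluded (exclusion 10) |
| Transplant recipient, graft artery affected | Excluded | Not eligible (inclusion 8) |
| Two kidneys, no transplant, one side affected | Excluded | No categorical exclusion |

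**Step 3: could another criterion close the last row?** Across the 11 inclusion and 20 exclusion criteria, two come near.
- Exclusion 11 covers severe organ-system disease and conditions judged to interfere with the child's health or the study. It does not name stenosis.
- Exclusion 12 applies only if a procedure affecting blood pressure, such as arterial repair, is likely during the study.

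Both are conditional; Section 6.2.1 is not.

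**Step 4: is the mention in 6.2.1 just loose phrasing?** The same sentence also names eGFR below 30 mL/min/1.73 m² and uncorrected aortic coarctation. Both were carried into Section 7.2 (exclusions 10 and 12). Only one-sided stenosis was not.

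**Step 5: what follows if such a child enters.**
- Arms giving an ARB: AZM-L, AZM-M, AZM-H and losartan, so 4 of 4.
- AZM-M, AZM-H and losartan step up at Week 2; AZM-L stays at 10 mg. In AZM-H the step is from 10 mg to 40 or 80 mg (Figure 8.a).
- The Week 2 visit has no laboratory test (Section 9.3.4.2). The first scheduled on-treatment renal panel is at Week 4; an earlier one is at the investigator's discretion (Section 6.1.4.1).
- Section 9.1.8.1 asks for repeat testing within about a week after a creatinine rise of 0.5 mg/dL, and withdrawal on a confirmed eGFR fall of more than 50% or to below 20. Section 7.5 item 1 allows termination for an adverse event.

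These safeguards act after exposure has begun. As an illustration, on an assumption not in the documents, let the affected kidney supply a share s of total eGFR and lose all function with no compensation by the other. The fall is then s, so with s ≤ 0.5 the fall does not exceed 50%. The other limit is reached when (1 − s) × baseline eGFR < 20. At s = 0.5 that needs a baseline below 20 / 0.5 = 40. The creatinine trigger or an adverse event might still prompt action.

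**Step 6: how many children.**
- Secondary-hypertension target: 0.20 × 213 = 42.6, so at least 43 children.
- Transplant cap: 0.25 × 213 = 53.25, about 53 children, all covered by inclusion 8.
- If every transplant recipient counts as secondary, 43 − 53 is negative, so transplant recipients could fill the whole target.

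The documents thus set no lower bound above zero on non-transplant children with secondary hypertension, and none on one-sided stenosis.

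**The case against.** The strongest reply is that the narrower wording may be the intended one. It appears twice and is specific, while Section 6.2.1 is the only outlier and sits in a justification section. If Section 7 governs, the defect is one inaccurate sentence and eligibility does not change. The documents do not settle this, so the point stands as far as intent goes. It does not remove the conflict. If one-sided disease is meant to be allowed, the stated renal rationale is wrong as it stands.

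A second reply is that other provisions narrow the group:
- exclusion 11 can be read as barring severe cardiovascular or genito-urinary disease whatever the investigator's opinion;
- inclusion 10 requires the treating physician to judge that withdrawal of treatment is safe;
- inclusion 11 sets laboratory conditions;
- exclusion 3 bars children on more than two antihypertensive drugs;
- the data monitoring committee reviews safety periodically.

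All of this is correct. None is a categorical bar on one-sided stenosis.

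Third, no affected child can be shown to exist. Section 6.2.1 does name renovascular disease, alongside renal parenchymal disease, as a leading cause of hypertension in infants and children. But the trial takes ages 6 to under 18 and at least 25 kg, and the same section says primary hypertension predominates in older children and adolescents. This limits the claim about size, not the claim that the rule is inconsistent.

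**Conclusion.** The concern holds. The current protocol text gives two incompatible rules for a non-transplant child with two kidneys and known one-sided renal artery stenosis, and the rule sites apply is the weaker one. The number affected is unknown and may be zero. If such a child is randomized, exposure to an ARB is certain (4 of 4 arms), and no on-treatment renal panel is scheduled before Week 4. Efficacy analyses, power and type I error are unaffected.

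The conclusion rests on reading the numbered criteria as deciding eligibility, which Sections 7.1, 9.1.14 and 9.3.4.1 support. It needs correcting despite the uncertain count because it bears on who may be enrolled, and the safety reason is the protocol's own.

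**What to change.** Amend exclusion criterion 10 and the matching item in the Study Summary to exclude known renal artery stenosis, unilateral or bilateral. Keep the present wording for other renovascular disease of both kidneys or a solitary kidney. If the sponsor means to admit one-sided disease with a normal second kidney, correct Section 6.2.1 and its rationale instead. Either way the texts must agree.

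The cost is wording in two places, or one under the alternative, and possibly the loss of a few children. No analysis changes.

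The amendment would catch known stenosis only. Table 9.b schedules no renal imaging, and Section 7.0 requires testing to classify hypertension only where necessary, so undiagnosed one-sided disease would still get through.
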